Bispectral Index: A Comparison of Bifrontal Montage Agreement

NCT04062240

May 19, 2019

General Study Information

Effective: 9/20/2017

Principal Investigator: [name]

Study Title: Bispectral Index: A Comparison of Bifrontal Montage Agreement

Protocol version number and date: version 1.0 - 5/19/2019

Research Question and Aims

Hypothesis: Bispectral index (BIS) sensors applied in a bilateral frontal montage will show similar readings for the duration of the study.

Aims, purpose, or objectives: The objective of this study is to determine measurement difference and variability of BIS values when monitored in a bilateral frontal montage. The results will be utilized to determine a sample size for further study.

Background (*Include relevant experience*, gaps in current knowledge, preliminary data, etc.): BIS monitors are FDA approved to gauge depth of sedation by analyzing segments of electroencephalogram (EEG) waves. The BIS monitor utilizes a proprietary algorithm to process the EEG information second by second, and outputs a number (0-100) that corresponds with a patient's level of consciousness. A level of 0 indicates no EEG activity; a level of 100 indicates awake EEG activity. Several studies demonstrated that BIS monitors may not be useful in paralyzed patients, as patients who were paralyzed and not sedated unexpectedly showed a large decrease in their BIS values following administration paralytic medications.²⁻⁴ Vivien et al² found BIS values dropped an average of 24 points in already sedated patients when the patients were given paralytics. In the same year, Messner and colleagues paralyzed unsedated volunteers and found a dramatic drop in BIS values until paralysis wore off or was reversed.³ Schuller et al⁴ repeated the Messner experiment and found similar results with 18 of 20 unsedated volunteer's BIS values dropping to levels expected of patients who were sedated. These results suggest that BIS monitors are integrating electromyography (EMG) data into its algorithm to derive a BIS value. Our hypothesis is that a BIS monitor commenced after paralysis, thereby lacking exposure to any "awake" EMG activity, will result in a cleaner data set and more accurate representation of a patient's level of sedation. Studying in this manner will require the subject to wear two BIS sensors in a frontal montage. The manufacturer of the sensors gives no guidance as to which side of the forehead an individual sensor is placed, and no studies demonstrate BIS validity with the use of concurrent sensors. The purpose of the present investigation is to assess the measurement difference and variability associated with use of concurrent bifrontal BIS sensors. The data obtained will be used as a framework for additional BIS study (separate IRB form to follow this research study).

Study Design and Methods

Methods: *Describe, in detail, the research activities that will be conducted under this protocol:*

We are proposing a nonrandomized, prospective, comparative, observational study in patients undergoing elective cardiac surgery with general anesthesia.

Patients will be screened for eligibility based the provided inclusion/exclusion criteria. Informed consent will be obtained.

The current standard of care in cardiovascular surgery calls for the placement of a BIS sensor to the patient's forehead per the manufacturer's recommendation on arrival to the operating room. The sensor is then connected to the BIS LoC2 module, which is connected to the BIS II module on the anesthesia monitor (Philips MX800). Our study will add an additional BIS sensor to the patient's forehead connected to a second monitor (Philips MX550) fitted with the same BIS LoC2 and BIS II modules as the anesthesia monitor. The sensors will be delineated as left (L) and right (R). The two monitors will be synced for time. After ensuring appropriate skin contact and signal quality of both sensors, BIS monitoring will commence. BIS readings will be available every 12 seconds during the 5 minute duration of the study. For the current analysis, data obtained from the BIS sensor at each interval will include BIS value, Signal Quality Index, EEG level, EEG Suppression Ratio, EEG asymmetry and Burst Suppression Level. Our primary interest, though, is the BIS value.

Potential limitations to the study include the following:

- Convenience sampling with no randomization
- Limited frequency of sampling (12 seconds) compared to other studies due to equipment limitations
- Manual transcription of data from monitor to data collection sheet; manual entry from data collection sheet to digital spreadsheet.

Resources: Describe the available resources to conduct the research (personnel, time, facilities, mentor commitment, etc.):

- The study will be performed in the cardiac operating room.
- [name] is the project advisor and primary investigator. He is available as needed for questions, guidance, and troubleshooting, and oversight.
- [name], CRNA is the faculty advisor for the project, serves as a liason between the clinical area, project advisor, and research activities. He helped find opportunities related to funding, and will provide guidance related to dissemination.
- [name], SRNA will obtain informed consent and perform all data gathering activities.
- Equipment
 - o BIS Quatro sensor (Medtronic, Dublin, Ireland)
 - o BIS LoC2 module (Medtronic, Dublin, Ireland)
 - o Intellivue MX550 monitor (Philips, Madison, WI)
 - o Intellivue MX800 monitor (Philips, Madison, WI)
 - o IntelliVue M1034B Bispectral Index BIS II Module (Philips, Madison, WI)

• The portable anesthesia transport monitor (Philips MX550) assigned to each operating room and fitted with the BIS LoC2 and BIS II modules will be used as the secondary monitor

Effective: 9/20/2017

- Statistical analysis will be performed with JMP software, with support provided by [name] from the Center for Clinical and Translational Science.
- Budget: This study has no budgetary needs as it utilizes already existing equipment and materials.
- A poster will be generated to disseminate results. Per institutional guidelines for poster development and preparation, Media Support Services will provide support and print the poster at no charge.

(1a) This is a multisite study involving Mayo Clinic and non Mayo Clinic sites. When checked, describe in
detail the research procedures or activities that will be conducted by Mayo Clinic study staff.
[(1b) Mayo Clinic study staff will be engaged in research activity at a non Mayo Clinic site. When checked,
provide a detailed description of the activity that will be conducted by Mayo Clinic study staff.

Subject Information

Target accrual is the proposed total number of subjects to be included in this study at Mayo Clinic. A "Subject" may include medical records, images, or specimens generated at Mayo Clinic and/or received from external sources.

Target accrual: 15 subjects

Subject population (children, adults, groups): adults undergoing elective cardiovascular surgery

Inclusion Criteria:

1. Adult patient having elective cardiac surgery.

Exclusion Criteria:

- 1. Patient refusal.
- 2. Pediatric patients.
- 3. Emergency procedure.
- 4. Patients with known or suspected carotid or cerebrovascular disease.
- 5. Patients with prior stroke.
- 6. Skin condition or anatomy preventing proper sensor placement.

Research Activity

Check all that apply and complete the appropriate sections as instructed.

CI	neek an that apply and complete the appropriate sections as instructed.			
1.	Drug & Device: Drugs for which an investigational new drug application is not required. Device for which (i) an investigational device exemption application is not required; or the medical device is cleared/approved for marketing and being used in accordance with its cleared/approved labeling. (Specify the Methods section)			
2.	☐ Blood : Collection of blood samples by finger stick, heel stick, ear stick, or venipuncture.			
3.	Biological specimens other than blood: Prospective collection of human biological specimens by noninvasive means that may include: urine, sweat, saliva, buccal scraping, oral/anal/vaginal swab, sputum, hair and nail clippings, etc.			
4.	Tests & Procedures: Collection of data through noninvasive tests and procedures routinely employed in clinical practice that may include: MRI, surface EEG, echo, ultrasound, moderate exercise, muscular strength & flexibility testing, biometrics, cognition testing, eye exam, etc. (Specify in the Methods section)			
5.	Data (medical record, images, or specimens): Research involving use of existing and/or prospectively collected data.			
6.	☐ Digital Record : Collection of electronic data from voice, video, digital, or image recording. (Specify in the Methods section)			
7.	Survey, Interview, Focus Group: Research on individual or group characteristics or behavior, survey, interview, oral history, focus group, program evaluation, etc. (Specify in the Methods section)			
	NIH has issued a Certificate of Confidentiality (COC). When checked, provide the institution and vestigator named on the COC and explain why one was requested.			
Biospecimens – Categories 2 and 3				
	Collection of blood samples. When multiple groups are involved copy and paste the appropriate section low for example repeat section b when drawing blood from children and adults with cancer.			
	a. From healthy, non-pregnant, adult subjects who weigh at least 110 pounds. For a minimal risk application, the amount of blood drawn from these subjects may not exceed 550ml in an 8 week period and collection may not occur more frequently than 2 times per week. Volume per blood draw:ml			
	Frequency of blood draw (e.g. single draw, time(s) per week, per year, etc.)			

b. From other adults and children considering age, weight, and health of subject. For a minimal risk application, the amount of blood drawn from these subjects may not exceed the lesser of 50 ml or 3 ml per kg in an 8 week period, and collection may not occur more frequently than 2 times per week. Volume per blood draw:ml
Frequency of blood draw (e.g. single draw, time(s) per week, per year, etc.)
(3) Prospective collection of biological specimens other than blood:
Review of medical records, images, specimens – Category 5
For review of existing data : provide a date range or an end date for when the data was generated. The end date can be the date this application was submitted to the IRB. Example: $01/01/1999$ to $12/31/2015$ or all records through $mm/dd/yyyy$.
Date Range:
Check all that apply (data includes medical records, images, specimens).
(5a) Only data that exists before the IRB submission date will be collected.
(5b) The study involves data that exist at the time of IRB submission and data that will be generated after IRB submission. Include this activity in the Methods section.
[(5c) The study will use data that have been collected under another IRB protocol. Include in the Methods section and enter the IRB number from which the research material will be obtained. When appropriate, note when subjects have provided consent for future use of their data and/or specimens as described in this protocol.
Enter one IRB number per line, add more lines as needed
☐ Data ☐ Specimens ☐ Data & Specimens
Data Specimens Data & Specimens
☐ Data ☐ Specimens ☐ Data & Specimens
[(5d) This study will obtain data generated from other sources. Examples may include receiving data from participating sites or an external collaborator, accessing an external database or registry, etc. Explain the source and how the data will be used in the Methods section.
(6) Video audio recording: Describe the plan to maintain subject privacy and data confidentiality, transcription, store or destroy, etc.

HIPAA Identifiers and Protected Health Information (PHI)

Protected health information is medical data that can be linked to the subject directly or through a combination of indirect identifiers.

Recording identifiers (including a code) during the conduct of the study allows you to return to the medical record or data source to delete duplicate subjects, check a missing or questionable entry, add new data points, etc. De-identified data is medical information that has been stripped of all HIPAA identifiers so that it cannot be linked back to the subject. De-identified data is **rarely** used in the conduct of a research study involving a chart review.

Review the list of subject identifiers below and, if applicable, check the box next to each HIPAA identifier being recorded at the time of data collection or abstraction. Identifiers apply to any subject enrolled in the study including Mayo Clinic staff, patients and their relatives and household members.

Internal refers to the subject's identifier that will be recorded at Mayo Clinic by the study staff. **External** refers to the subject's identifier that will be shared outside of Mayo Clinic.

Check all that apply:	INTERNAL	EXTERNAL
Name		
Mayo Clinic medical record or patient registration number, lab accession,	X	
specimen or radiologic image number		
Subject ID, subject code or any other person-specific unique identifying	X	
number, characteristic or code that can link the subject to their medical data		
Dates: All elements of dates [month, day, and year] directly related to an	X	
individual, their birth date, date of death, date of diagnosis, etc.		
Note: Recording a year only is not a unique identifier.		
Social Security number		
Medical device identifiers and serial numbers		
Biometric identifiers, including finger and voice prints, full face photographic		
images and any comparable images		
Web Universal Resource Locators (URLs), Internet Protocol (IP) address		
numbers, email address		
Street address, city, county, precinct, zip code, and their equivalent geocodes		
Phone or fax numbers		
Account, member, certificate or professional license numbers, health		
beneficiary numbers		
Vehicle identifiers and serial numbers, including license plate numbers		
Check 'None' when none of the identifiers listed above will be recorded,	None	None None
maintained, or shared during the conduct of this study. (exempt category 4)	Trone	Markette

Data Analysis

Power analyses may not be appropriate if this is a feasibility or pilot study, but end-point analysis plans are always appropriate even if only exploratory. Provide all information requested below, or provide justification if not including all of the information.

Power Statement: The sample-size for this investigation was determined after weighing statistical considerations along with the logistical and resource constraints inherent in the study design. A sample-size of 15 patients will provide a total of 450 paired data-points that will be used for the analysis.

Data Analysis Plan: For each patient, 30 data points will be obtained for each parameter monitored per BIS sensor. The agreement between (L) and (R) sensors will be assessed using the methods of Bland and Altman, as Bland-Altman plots allow identification of any systematic difference between measurements and possible outliers.⁴

Endpoints

Primary: Difference and variability of BIS values obtained from (L) and (R) sensors.

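### The study is meant to supply a sample-size input, but the plan neither separates between- from within-patient variability nor puts an interval on the SD, and its 450 pairs come from 15 patients

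*Combined protocol and SAP*

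**What the plan says.** Under Research Question and Aims, the objective is to "determine measurement difference and variability of BIS values when monitored in a bilateral frontal montage", and the next sentence gives the use: "The results will be utilized to determine a sample size for further study". The Background adds that the data will serve as a framework for another BIS study under a separate IRB form.

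The size is set under Subject Information: "Target accrual: 15 subjects". The Power Statement explains it in general terms: "The sample-size for this investigation was determined after weighing statistical considerations along with the logistical and resource constraints inherent in the study design". It then says: "A sample-size of 15 patients will provide a total of 450 paired data-points that will be used for the analysis". The Data Analysis Plan states "For each patient, 30 data points will be obtained for each parameter monitored per BIS sensor" and "The agreement between (L) and (R) sensors will be assessed using the methods of Bland and Altman".

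The Endpoints list the difference and variability of BIS values between the left and right sensors as primary. Nothing further is said about which SD will be calculated, how the repeated readings within a patient enter it, or how its uncertainty will be shown.

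**The concern.** A left-right difference has two sources of variation. Some patients will have a consistent offset between sides (between-patient), and within any patient the difference will move from reading to reading (within-patient). A follow-on study analysed by patient needs the SD of a per-patient summary, which is driven mainly by the first source once 30 readings are averaged.

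A Bland-Altman analysis of 450 pooled pairs gives one SD that mixes the two. A later reader could not recover the SD of patient-mean differences from it. The figure of 450 would also invite that reader to treat the SD as much better known than 15 patients allow. In either case the study would not clearly deliver the sizing input that its Aims name.

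**Working it through.** **Inputs from the documents.** 15 patients (Subject Information); 30 readings per patient and 450 pairs (Data Analysis); one reading every 12 seconds for 5 minutes (Methods).

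**Assumptions, not in the documents.** Normal data; a common intraclass correlation (ICC, the between-patient share of the total variance of the left-right difference), shown over a range.

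**1. The plan's own figure.** 15 × 30 = 450, which reproduces. The Methods, however, say "BIS readings will be available every 12 seconds during the 5 minute duration of the study". That is 300 / 12 = 25 readings per patient, or 375 pairs (26 and 390 if both ends are counted). The two sections need reconciling, but the number of patients, and so the 14 df, is unaffected.

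**2. Precision of the SD.** The 95% interval for the true SD is s × √(df/χ²₀.₉₇₅) to s × √(df/χ²₀.₀₂₅).
- Patient level, df = 15 − 1 = 14: √(14/26.12) = 0.73 and √(14/5.63) = 1.58.
- If 450 pairs were independent, df = 449: √(449/509.60) = 0.94 and √(449/392.18) = 1.07.

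**3. What a pooled SD estimates.** Set the total variance to 1. The variance of a patient mean is M = ICC + (1 − ICC)/30. The expected pooled variance is P = [14 × 30 × M + 435 × (1 − ICC)] / 449, where 435 = 15 × 29. The ratio of pooled SD to patient-mean SD is √(P/M).

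| ICC | M | P | √(P/M) | P/M |
|---|---|---|---|---|
| 0.7 | 0.710 | 0.955 | 1.16 | 1.34 |
| 0.5 | 0.517 | 0.968 | 1.37 | 1.87 |
| 0.3 | 0.323 | 0.981 | 1.74 | 3.03 |
| 0.1 | 0.130 | 0.994 | 2.76 | 7.64 |

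Sample size for a comparison of means is proportional to the variance. The last column is therefore the factor by which a follow-on study of patient means would be over-sized, on average, if the pooled SD were used.

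**4. Coverage of an interval on 449 df.** In 40,000 simulated studies of 15 × 30 readings at each ICC, a nominal 95% interval for the single-reading SD built on 449 df covered the true value in about 69% of studies at ICC 0.3, 49% at 0.5 and 37% at 0.7.

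**5. For information: an unadjusted patient-level SD.** Assume the follow-on is sized on per-patient differences by normal theory, with two-sided alpha 0.05, nominal power 80% and the same true SD σ. Realised power is Φ(2.80 × s/σ − 1.96), with 14s²/σ² following χ² on 14 df. Mean power is 76% and median power 78%. Power falls below 70% when s/σ < (1.96 + 0.524)/2.80 = 0.887, that is when χ² < 14 × 0.887² = 11.01, which has probability about 31%.

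**The case against.** The strongest reply is that the plan commits to none of the faulty steps. It counts 450 pairs but does not claim that they are independent, and it states no SD precision. It does not say that a pooled or unadjusted SD will be carried forward. The follow-on study has its own protocol, where alpha, power, endpoint and any inflation of the SD belong. For an exploratory study of 15 patients, a short analysis plan is understandable.

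Much of this stands, and it rules out a stronger reading. A reader might infer that the follow-on study would probably be under-powered, because a sample SD on 14 df falls below the true SD 55% of the time. The documents do not support that as a criticism of this plan:
- No section says that an unadjusted SD will be used.
- The 55% is not special to 15 patients: it is 53.5% with 30 and 52.7% with 50.
- The typical shortfall is small (median power 78% against 80%).
- The direction is not fixed. A pooled SD used to size patient means would usually give a study that is too large, unless the ICC is about 0.9 or more.

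For the same reasons, no particular inflation formula should be written into this plan. The choice is a trade-off for the follow-on protocol.

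The reply does not remove the reporting gap. Supplying a sizing input is an aim of this study, and only this study can report its two variance components and their uncertainty. The form's own instructions ask for an end-point analysis plan even in exploratory work.

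**Conclusion.** The concern holds as a gap in the analysis plan. Variability is part of the primary endpoint and is to feed a sample-size calculation, yet the plan does not say which variability or how well it will be known.

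The patient-level SD will be known only to within 0.73 to 1.58 times its estimate; the count of 450 could be misread as 0.94 to 1.07. This contrast rests on normality and on patients being independent. It does not depend on the ICC, on correlation between successive readings, or on whether there are 25 or 30 readings per patient. The 1.16 to 2.8 ratio of pooled to patient-mean SD does depend on the ICC, which the documents do not give, and on readings being equally correlated within a patient. The power figures in step 5 rest on a follow-on design that the documents do not state, and only illustrate why the interval matters.

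**What to change.** Add to the Data Analysis Plan, for the BIS value and, where the scale permits, the secondary parameters:

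> The left-minus-right difference will be analysed by a Bland-Altman method for repeated measures, based on a one-way variance-components model with patient as the random factor. The SD of the patient-mean difference (14 df with 15 patients) and the within-patient SD will each be reported with a 95% confidence interval. Precision for patient-level quantities rests on 15 patients, not on the number of paired readings.

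Successive readings 12 seconds apart may be correlated. If so, an interval for the within-patient SD on 15 × 29 = 435 df would be too narrow, and the report should say so. The patient-mean SD does not have this problem.

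In the Power Statement, give the number of pairs together with the statement that they are clustered in 15 patients, and reconcile 30 readings with the 12-second interval over 5 minutes. Leave any inflation of the SD to the follow-on protocol.

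The cost is a little more analysis work and wider stated intervals. No extra patients, readings or procedures are needed.

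### Forehead side is not balanced against monitor and the L–R analysis has no monitor term, so a side difference cannot be told apart from an offset between the MX800 and MX550 chains

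*Combined protocol and SAP*

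**What the plan says.** The Methods section describes two measurement chains. On arrival in the operating room the usual-care sensor is connected through a LoC2 module and a BIS II module to the anesthesia monitor, a Philips MX800. The study adds a second sensor "connected to a second monitor (Philips MX550) fitted with the same BIS LoC2 and BIS II modules as the anesthesia monitor". The Resources section identifies this second device as "The portable anesthesia transport monitor (Philips MX550) assigned to each operating room" and gives it the role of secondary monitor. The added sensor therefore always reads on an MX550, and the physical unit may differ between rooms.

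The sensors are labelled L and R. No text says which side is connected to which monitor, or that this is fixed, alternated or randomised. The Background notes that "The manufacturer of the sensors gives no guidance as to which side of the forehead an individual sensor is placed", so usual care does not settle the side either. The data listed for each interval are six sensor outputs; the side–monitor pairing is not among them. The checks described are time synchronisation, skin contact and signal quality. No comparison of the two chains is planned.

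Under Data Analysis Plan, "The agreement between (L) and (R) sensors will be assessed using the methods of Bland and Altman", with no monitor term. The primary endpoint is "Difference and variability of BIS values obtained from (L) and (R) sensors". The Aims add: "The results will be utilized to determine a sample size for further study".

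**The concern.** Two things differ within every pair: the side of the forehead and the chain. Here "chain" means the monitor, the individual module units and the usual-care or added status of the sensor, taken together. The endpoint is read as bifrontal montage agreement, that is, as a property of side. If one chain reads systematically higher, the planned analysis has no means of saying so.

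The effect depends on a placement pattern that the protocol leaves open.

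- With constant placement, the offset goes entirely into the mean L–R. It could pass for a side difference or hide a real one of opposite sign. No later analysis and no additional patients placed the same way could separate the two.
- With mixed placement and no chain term, the offset moves out of the mean and into the SD. It then widens the limits of agreement and enters the SD carried into planning the next study.
- With mixed placement that is written down, the two effects can be separated. The plan secures neither the mixing nor the record.

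**Working it through.** **The plan's own figure.** 15 patients × 30 readings = 450 pairs, as the Power Statement says. No swap of chains within a patient is described, so the pairing is taken as constant within patient. For this question the independent units are the 15 patients, not the 450 pairs.

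**Model.** For patient i, the mean L–R difference is D_i = side + d·x_i + e_i. Here x_i = +1 if L is on the MX800 and −1 if R is; d is the MX800-minus-MX550 chain offset; e_i has SD s. With p the share of patients with L on the MX800:

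- expected mean L–R = side + (2p − 1)d
- variance of D = s² + 4p(1 − p)d²

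The documents give neither d nor s. I assume s = 5 BIS points and show d = 1, 2, 3 and 5. The model takes d as the same in all patients.

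**Effect on the mean and SD without a chain term**

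| p | Bias in mean L–R (d = 1, 2, 3, 5) | SD of D (d = 1, 2, 3, 5) |
|---|---|---|
| 1 | 1, 2, 3, 5 | 5.00 throughout |
| 0.8 | 0.6, 1.2, 1.8, 3.0 | 5.06, 5.25, 5.55, 6.40 |
| 0.5 | 0 throughout | 5.10, 5.39, 5.83, 7.07 |

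Example for p = 0.8, d = 3: bias = 0.6 × 3 = 1.8; SD = √(25 + 0.64 × 9) = √30.76 = 5.55. At p = 0.5 the variance rises by 4%, 16%, 36% and 100%.

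With 15 patients the nearest to balance is 8/7. The offset's weight in the unadjusted mean is then (8 − 7)/15 = 0.067, against 1.00 at 15/0.

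**Sampling error of the SD.** From 15 patient-level differences (chi-square, 14 df) the 95% interval for an SD runs from 0.73 to 1.58 times the estimate. SD inflation for d up to 3 (at most 5.83/5 = 1.17) lies well inside that.

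**Precision of the side effect with a chain term.** SE(side)/s = 1/√[15(1 − x̄²)], where x̄ is the mean of x_i.

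| Split | x̄ | SE(side)/s |
|---|---|---|
| no chain term | – | 1/√15 = 0.258 |
| 8/7 | 0.067 | 0.259 |
| 12/3 | 0.600 | 0.323 (+25%) |
| 14/1 | 0.867 | 0.518 (doubled) |
| 15/0 | 1.000 | not estimable |

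Recording the pairing without balancing it is thus the weaker safeguard.

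**95% half-width for the side effect at s = 5**

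- No chain term: 2.145 × 0.2582 × 5 = 2.77 points (14 df).
- 8/7 with chain term: 2.160 × 0.2588 × 5 = 2.80 points (13 df).

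**The case against.** The strongest reply is that the study wants the total disagreement between two concurrent sensors, equipment included. The Background supports that reading: it speaks of the use of concurrent bifrontal sensors and says the next study needs two of them. On that view the total SD is the right input. This stands in part. The follow-on montage is stated but its hardware is not, so which SD will be wanted is still open. The mean difference would also still be reported as left against right.

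The offset may well be small. The module types are the same, and no figure in the documents supports any value of d. That stands, and the d = 5 column is only illustrative. But the same type is not the same unit, and no check of equivalence is described.

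Fifteen patients measure little here. At s = 5, a bias of 1 or 2 points is smaller than the 2.77-point half-width. Even at 8/7 the chain effect has an SE of 0.2588 × 5 = 1.29; power to detect it (two-sided 5%, 13 df) is about 11%, 30% and 57% for d = 1, 2 and 3. That also stands. The change removes a bias; it will not reliably show whether an offset exists.

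Constant placement leaves the SD unchanged only if d is constant. With a different MX550 in each room, unit differences enter the SD, and a single pairing term leaves them in the residual. This is correct and limits what the residual SD means.

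Finally, the person collecting the data will know the pairing, and the data sheet itself is not in the documents, so it may in practice be written down. That is fair, but the protocol does not require it, and a record does not produce balance. The disclosed lack of randomisation concerns how patients are sampled and does not cover this point.

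**Conclusion.** The concern holds. Nothing in the protocol separates a side difference from a chain offset: there is no allocation rule, no stated record of the pairing and no term in the analysis. Complete aliasing follows only if placement never varies, which the documents do not state; otherwise it is partial.

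The possible bias in the mean runs from almost nothing near balance to the whole of d at constant placement, and d is unknown. The effect on the SD is minor for modest offsets at this sample size. The main loss is correct attribution of the mean L–R difference, which is half of the primary endpoint. Confidence is high that the gap exists; its practical size cannot be judged from the documents. The change is worth making because it is cheap, not because a large offset has been shown.

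**What to change.** 1. Before enrolment, prepare a list that alternates or randomises which side is connected to the MX800, 8/7 over the 15 patients.
2. Record on the data sheet the side–monitor pairing and the operating room or monitor unit.
3. Fit the pairing as a fixed effect in the model for the L–R difference, with patient as the independent unit. Report the side and chain effects with their intervals.
4. Report both the total two-chain SD and the residual SD after the pairing term, so that the follow-on study can use the one that matches its equipment. State that unit-to-unit differences between rooms remain in the residual.

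The cost is a 15-line list, one or two data fields, one model term and one degree of freedom, with no extra patients, sensors or staff. The drawback is that the list would dictate the side of the usual-care sensor in a study described as nonrandomized and observational. If the investigators do not want that, they should still record the pairing and describe the endpoint as agreement between two side-plus-monitor chains, not between left and right.

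### Thirty readings per patient cannot be obtained at 12-second intervals in 5 minutes: the stated design gives 25 per patient and 375 pairs, not 450

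*Combined protocol and SAP*

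**What the plan says.** Four places in the combined protocol and SAP bear on the number of readings.

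- **Study Design and Methods, Methods** sets the sampling interval and the recording window together: "BIS readings will be available every 12 seconds during the 5 minute duration of the study".
- **The list of potential limitations in the same section** gives the interval again, with its cause: "Limited frequency of sampling (12 seconds) compared to other studies due to equipment limitations".
- **Subject Information** sets the number of patients: "Target accrual: 15 subjects".
- **Data Analysis** gives the expected yield. The Data Analysis Plan says: "For each patient, 30 data points will be obtained for each parameter monitored per BIS sensor". The Power Statement says: "A sample-size of 15 patients will provide a total of 450 paired data-points that will be used for the analysis".

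No section gives another interval, a longer recording, or additional readings.

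**The concern.** The count in the Data Analysis section does not follow from the interval and window in the Methods. Thirty readings at 12-second spacing do not fit into 5 minutes.

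Two things are at stake. First, 450 is the only data-yield figure offered alongside the choice of 15 patients. The rest of the Power Statement refers in general terms to statistical and practical considerations, with no standard deviation, precision target or power. If the one number is wrong, the reader is misinformed about how much data will stand behind the variability estimates, and those estimates are meant to size a further study.

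Second, the conflict reaches data collection. Readings are transcribed by hand from the monitor. A collector can stop at 5 minutes with 25 or 26 rows, or continue until there are 30; the protocol does not say which instruction governs. If practice varied, the observation window and the number of readings would differ between patients. A complete 5-minute record would also appear to have missing readings when compared with the planned 30, and so be hard to tell apart from real loss.

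**Working it through.** **Inputs**

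| Quantity | Value | Source |
|---|---|---|
| Sampling interval | 12 s | Methods; repeated in the limitations |
| Recording window | 5 min = 300 s | Methods |
| Patients | 15 | Subject Information; Power Statement |
| Stated readings per patient, per parameter, per sensor | 30 | Data Analysis Plan |
| Stated pairs | 450 | Power Statement |

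**Step 1: reproduce the plan's figure.** 15 × 30 = 450, and 450 / 15 = 30. The two Data Analysis figures agree with each other, so the discrepancy lies in the 30 readings, or in the interval or window, and not in the multiplication or the patient count.

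**Step 2: derive the yield from the Methods.** Readings per patient = window / interval.

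| Counting convention | Readings per patient | Pairs from 15 patients | Shortfall against 450 |
|---|---|---|---|
| First reading at 12 s | 300 / 12 = 25 | 15 × 25 = 375 | 75; 75 / 450 = 16.7% |
| Time zero also counted | 25 + 1 = 26 | 15 × 26 = 390 | 60; 60 / 450 = 13.3% |

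Neither convention gives 30 or 450. Put the other way, the stated count is 20% above 375 (450 / 375 = 1.20) and about 15% above 390 (450 / 390 = 1.154).

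**Step 3: what would be needed for 30 readings.**

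- At 12 s spacing: 30 × 12 s = 360 s = 6 min. With time zero counted, 29 × 12 s = 348 s = 5.8 min.
- In 5 min: 300 / 30 = 10 s spacing. With time zero counted, 300 / 29 ≈ 10.3 s.

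The shorter spacing conflicts with the equipment limitation that the protocol itself reports. The longer window appears nowhere in the document.

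**Step 4: other readings of the text.** The 30 cannot be a total over parameters or over the two sensors, because the Data Analysis Plan states it per parameter and per sensor.

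**Step 5: effect on precision.** The documents give no within-patient correlation, so this rests on an assumption: equally correlated left-minus-right differences within a patient, with intraclass correlation ρ. The variance of the mean difference is then proportional to ρ + (1 − ρ)/m for m readings per patient. Comparing m = 25 with m = 30:

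| Assumed ρ | m = 25 | m = 30 | Increase in standard error |
|---|---|---|---|
| 0 | 0.0400 | 0.0333 | √1.200 − 1 = 9.5% |
| 0.1 | 0.1360 | 0.1300 | √1.046 − 1 = 2.3% |
| 0.5 | 0.5200 | 0.5167 | √1.006 − 1 = 0.3% |

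**The case against.** The strongest reply accepts the arithmetic and disputes its weight.

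- **Which figure is the slip is not settled.** Since 30 and 450 agree with each other, the 5-minute window could be the error. This stands: the documents do not show which number was intended, and the correction has to allow for either. It does not remove the contradiction.
- **The sample size is 15 patients, and 450 is only what they are expected to yield.** This also stands. No power, significance level or precision target depends on 450, and a pilot need not have a power calculation. Still, the Power Statement presents 450 as the number of pairs that will be analysed, and the Methods do not produce it.
- **The statistical effect is small.** Correct. The standard error of the mean difference would rise by at most 9.5% under the assumption above, and by far less if readings within a patient are correlated, as readings 12 seconds apart probably are. The point does not rest on lost precision.
- **The operational harm is conjectural.** In part. The data collection sheet is not in the documents, and one person gathers all the data, which makes differing windows between patients less likely. They remain possible, because the instructions cannot both be followed.

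**Conclusion.** The point holds. With the interval and window in the Methods, the study yields 25 readings per sensor per patient and 375 pairs, or 26 and 390 if a time-zero reading is counted. The stated 30 and 450 are not reached under either convention, and these yields already assume 15 evaluable patients and no lost reading. The conclusion uses only figures in the document. The accrual target, the endpoints and the choice of a Bland–Altman analysis are unaffected. The correction is needed because the stated yield is wrong for the stated design and the collection instructions conflict.

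**What to change.** Choose one of the following before data collection, and carry it through the Methods, the Power Statement and the Data Analysis Plan.

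1. **Keep 5 minutes at 12 seconds.** Restate the yield as 25 data points per parameter per sensor for each patient and 375 pairs, or as 26 and 390 if the time-zero reading is kept.
2. **Keep 30 and 450.** Change the stated recording to 6 minutes, with the first reading at 12 seconds. If a time-zero reading were kept as well, 6 minutes would give 31 per patient and 15 × 31 = 465 pairs.

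In either case, state whether time zero counts and when recording stops, and match the data collection sheet to that rule.

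The first option costs only wording and a smaller stated count. The second adds one minute of passive recording per patient, 15 minutes over the whole study. Neither changes the number of patients or the analysis method.
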